5. High-risk + multi-fact: Messages informing them that they are at high risk for shingles because they are ages 50+, with additional facts about shingles and the shingles vaccine, and encouraging them to ask about the vaccine at their upcoming appointment.

Patients were additionally randomized to one of the following message **frequency** conditions:

1. Two messages: Messages 3 days and 1 day before the appointment
2. Three messages: Messages 3 days, 2 days, and 1 day before the appointment

Finally, patients were randomized to one of the following **cost** conditions:

1. Cost Omitted: the cost of the vaccine was not mentioned in the final message 1 day prior to the appointment

2. Cost Mentioned: The cost of the vaccine was mentioned in the final message 1 day prior to the appointment.
 - a. In this arm, cost messages varied by whether the patient was a Geisinger Health Plan (GHP) member in a plan that allowed them to get the vaccine at no cost (the vast majority of GHP members):
 - i. Eligible GHP members were told that they could get the vaccine at no cost
 - ii. Those without GHP (and the few GHP members for whom the vaccine was not definitively covered at no cost) were told that “most patients” could get the flu vaccine at no cost

Patients were randomized on the phone number level, so patients who shared a phone number were sent the same message version.

Power Analysis

The baseline vaccination rate is 4.1% (i.e., the rate of patients not vaccinated against shingles who get a vaccine at a given eligible appointment). With 50,000 patients, and 10,000 patients per arm, we have 80% power to detect an increase in shingles vaccination rates of 0.8 percentage points, 4.1% to 4.9%, with two-tailed alpha = .05 for any comparison between message arms.

Project Status

Enrollment surpassed 50,000 patients on 6/8/2025, and as described below, we continued enrolling non-GHP patients after reaching that target. However, Geisinger decommissioned the text messaging platform that the study was running at the end of June 2025, 15 days short of our intended non-GHP extension and we ended the trial at that time. Our last day of enrolling new patients was 6/27/2025 for appointments on 6/30/2025, and our final sample size was 50,785 patients.

We have not yet extracted outcome data as of this writing.

Past Project Status Notes

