Analysis 3 (Exploratory): We will run an OLS regression to test whether vaccination is different as a function of the number of messages patients were sent (0 = patient was randomized to be sent two messages; 1 = patient was randomized to be sent three messages). This analysis will be limited to patients randomized to a message arm (active control, high risk, multi-fact, high risk + multi-fact).

Other Pre-specified Outcomes

We will run the analyses described above on the following additional outcomes:

1. First shingles vaccination [Time Frame: In the 10 days following enrollment]

Received a first shingles vaccination in the 10 days following enrollment (y/n)

2. Attended scheduled appointment [Time Frame: 3 days after enrollment]

Attended the target vaccine-eligible appointment (y/n)

3. First shingles vaccination [Time Frame: In the 14 months following enrollment]

Received a first shingles vaccination in the 14 months following enrollment (y/n)

4. Time to first shingles vaccination [Time Frame: In the 14 months following enrollment]

Number of days between enrollment and first shingles vaccination

5. Completion of shingles vaccine series [Time Frame: In the 14 months following enrollment]

Completed shingles vaccination series by getting a second shingles vaccination (y/n)

6. Time to completion of shingles series [Time Frame: In the 14 months following enrollment]

Number of days between first and second shingles vaccination

7. Shingles diagnosis [Time Frame: In the 14 months following enrollment]

Diagnosed with shingles (y/n)

As with the primary outcome, we will collect both EHR and claims data to support other pre-specified outcomes (vaccination and diagnosis). We will use a 91-day lag to allow sufficient time for claims to be processed.

Exploratory analysis with the primary outcome

1. Interaction between including risk and facts

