The four active arms in the study are a pragmatic 2x2 design, where two arms contain risk information (high-risk, high-risk + multi-fact) and two arms include facts about the shingles vaccine (multi-fact, high-risk + multi-fact); one arm (active control) does not include either risk information or facts. We will run an OLS regression testing for an interaction between risk information and facts. The dependent variable will be the primary outcome of vaccination at the target appointment. The independent variables will be risk information (0 = no high-risk information, 1 = high risk information) and facts (0 = no facts about shingles or the vaccine, 1 = facts about shingles and the vaccine), and the interaction between risk information and facts variables. This analysis will be limited to patients who were in a message arm (active control, high risk, multi-fact, high risk + multi-fact).

2. All 2-, 3-, and 4-way interactions between risk, facts, cost, and frequency

We will run OLS regressions to explore whether any 2-, 3-, or 4-way interactions are significant between messages that include risk, facts, cost information, and message frequency. Although these analyses will be underpowered, any significant findings may inform hypotheses for future interventions. These analyses will be limited to patients who were in a message arm (active control, high risk, multi-fact, high risk + multi-fact).

3. Effects of different cost messages

Among patients assigned to get messages that mention the vaccine cost, GHP members were told they could get the vaccine at no cost. Patients who were not GHP members were told that *most* patients can get the vaccine at no cost. We will run an OLS regression to test for an interaction between cost message (cost omitted, cost mentioned) and insurance group (GHP members, non-GHP members), among patients who were in a message arm (active control, high risk, multi-fact, high risk + multi-fact).

Analysis Notes

The primary analyses described above will be intent-to-treat, but we may run follow-up robustness checks limited to patients for whom messages were delivered successfully according to messaging data.

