Because patients were randomized at the phone number level, we will choose one patient per phone number to include in the primary analysis. If patients with the same phone number were enrolled on different days, we will include the first patient enrolled. If patients were enrolled on the same day, GHP members will be prioritized for inclusion. If all patients with the same phone number and appointments on the same day were in the same insurance group (GHP or non-GHP), we will randomly choose a patient to include. We may run follow-up robustness checks including all patients.

Recent work suggests that OLS regressions are appropriate in randomized experiments with binary outcome variables such as ours (Gomila, 2021).

For analyses of vaccine timing other pre-specified outcomes (time to first shingles vaccination and time to completion of shingles series), we will examine the outcome distribution before choosing an appropriate regression model (likely negative binomial or Poisson regression).

For all analyses, we will report heteroskedasticity-robust standard errors.

We plan to run exploratory analyses to understand heterogeneity in observed effects (e.g., in demographic covariates such as age, sex, race, whether the patients were GHP members).

Reference

Gomila, R. (2021). Logistic or linear? Estimating causal effects of experimental treatments on binary outcomes using regression analysis. *Journal of Experimental Psychology: General*, 150(4), 700–709. <https://doi.org/10.1037/xge0000920>

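### The two vaccine-timing outcomes have no value for patients without the dose(s), and the SAP gives no rule for them, so as written arms would be compared within a post-randomisation subset

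*SAP*

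**What the plan says.** Under Other Pre-specified Outcomes, the SAP states: "We will run the analyses described above on the following additional outcomes". Item 4 is "Number of days between enrollment and first shingles vaccination" and item 6 is "Number of days between first and second shingles vaccination", each with a 14-month time frame. The analyses carried over are the arm comparison (four contrasts with passive control), the cost comparison and the frequency comparison. That is (4 + 1 + 1) × 2 = 12 contrasts for the two timing outcomes.

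The only method given for them is in the Analysis Notes: "we will examine the outcome distribution before choosing an appropriate regression model (likely negative binomial or Poisson regression").

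The same section says "The primary analyses described above will be intent-to-treat". It does not say how a patient without a dose enters a timing analysis.

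**The concern.** A patient who never receives a first dose has no number of days for outcome 4. A patient who does not receive two doses has none for outcome 6. A Poisson or negative binomial regression needs a number for each patient, so without a rule the others drop out.

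Those who remain are defined by an event after randomisation, and it is the event the messages aim to produce. The ratio of mean days in that subset mixes who was vaccinated with when they were vaccinated. Randomisation no longer protects it. What is at stake is a statement that messages speed up or slow down vaccination, or leave its timing unchanged, when the figure reflects a change in who is counted.

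The model family is not the fault. The same family applied to capped time in all patients would give a valid comparison.

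**Working it through.** **The plan's own figure.** The SAP powers only the vaccination rate: 4.1% vs 4.9%, 10,000 per arm, two-sided 5%, 80% power. SE = √[(0.041×0.959 + 0.049×0.951)/10,000] = 0.00293, and 0.008/0.00293 − 1.96 = 0.77, which is 77.9% power. The difference detectable at exactly 80% is 0.82 points, which rounds to the stated 0.8. The SAP gives no figure for the timing outcomes.

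**Inputs for outcome 4.** From the SAP: p = 4.1% (control) and 4.9% (message) vaccinated at the appointment, 3 days after enrollment; 10,000 per arm; a 14-month window. Assumed, because the SAP gives none: later uptake L, with later doses spread evenly over days 4–425 (mean 214.5), and 14 months taken as 426 days.

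**Formulas.**
- Mean days among vaccinated = (3p + 214.5L)/(p + L). The ratio of these means is the Poisson or negative binomial estimate with arm as the only predictor. SE of the log ratio = √Σ[var/(number vaccinated × mean²)].
- Difference in mean capped days, all patients = −(423Δp + 211.5ΔL), because 426 − 3 = 423 and 426 − 214.5 = 211.5. Its SE uses unequal variances.
- Outcome 3: difference in p + L, unpooled SE.

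**Example, L = 3% in both arms.**
- Means: (0.041×3 + 0.03×214.5)/0.071 = 92.4 and (0.049×3 + 0.03×214.5)/0.079 = 83.3. Ratio 0.90.
- SE of the log ratio, with SDs of 131.1 and 127.2 days in 710 and 790 patients, is 0.076. So z = −0.103/0.076 = −1.36, and a significant ratio below 1 occurs in 27% of trials.
- Capped difference: −423×0.008 = −3.38 days, SE 1.36, power 70%.

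| Later uptake, control vs message | Mean days, vaccinated only | Ratio | Vaccinated only: significantly faster | Capped difference, all (days) | Capped time: power | Outcome 3: power | Control with no value |
|---|---|---|---|---|---|---|---|
| (a) 3% vs 3% | 92.4 vs 83.3 | 0.90 | 27% | −3.38 | 70% | 57% | 93% |
| (a) 6% vs 6% | 128.6 vs 119.4 | 0.93 | 33% | −3.38 | 64% | 45% | 90% |
| (a) 10% vs 10% | 153.0 vs 144.9 | 0.95 | 34% | −3.38 | 58% | 36% | 86% |
| (a) 20% vs 20% | 178.5 vs 172.9 | 0.97 | 30% | −3.38 | 47% | 26% | 76% |
| (b) 3% vs 4% | 92.4 vs 98.1 | 1.06 | 0.2% (slower in 13%) | −5.50 | 98% | above 99% | 93% |
| (c) 3% vs 2.2% | 92.4 vs 68.5 | 0.74 | 94% | −1.69 | 24% | 2.5% | 93% |

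In (b) the message arm has more patients vaccinated at every time point from day 3, yet the vaccinated-only ratio exceeds 1. In (c) messages only bring doses forward: 4.1% + 3% and 4.9% + 2.2% are both 7.1%.

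**When the ratio passes 1.** The mean among vaccinated patients depends only on L/p. With 4.1% and 4.9% on the day, the ratio exceeds 1 once later uptake rises by more than 4.9/4.1 − 1 = 19.5% in relative terms, for example from 3% to above 3.59%.

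**Outcome 6.** No figure is computed. Its clock starts at the first dose, so the interval stays conditional on a post-randomisation event even if follow-up is capped. The cost and frequency contrasts are not computed either; the same reasoning applies to them.

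**The case against.** **The fault is inferred.** A reader might conclude that the SAP plans to analyse vaccinated patients only. It does not say so: no population is named for the timing outcomes, and the model is only called likely. The 14-month frame could serve as a cap, but nothing assigns it to patients without a dose. Even if the intent-to-treat sentence is read to cover these outcomes, it gives such patients no number. What stands is a missing rule whose natural execution is a subset comparison.

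**The consequence is small.** A reader might also infer that the trial could miss a benefit. The SAP does not support that. Only Analysis 1 is labelled confirmatory, and outcomes 1, 3 and 5 compare 10-day uptake, 14-month uptake and completion in everyone. A misleading timing ratio would sit beside valid comparisons. This stands.

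**A reversal needs a strong assumption.** With equal later uptake the ratio points the right way, and a significant result in the wrong direction occurs in under 0.1% of trials. Case (b) needs later uptake to rise by a third, more than the 19.5% gain on the day, from messages sent 1 to 3 days before one appointment. This limits how likely a reversal is. It does not make the ratio a measure of speed, because its size and direction still depend on who was vaccinated.

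**Capped time also mixes uptake and timing.** In (a), the −3.38 days are exactly the uptake gain times the days left to the cap. This is true, but it compares the groups as randomised. If messages only bring doses forward, capped time has far less power (24% vs 94%), which is a real price.

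**Conclusion.** The point holds as a gap that should be closed, at moderate importance. As written, the arm, cost and frequency comparisons on outcomes 4 and 6 would be made within a subset formed after randomisation and could not be read as an effect of the messages on speed. This affects two of seven other pre-specified outcomes and leaves the primary analysis untouched.

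The figures illustrate outcome 4 for one contrast of 10,000 per arm. They rest on the SAP's 4.1% and 4.9% and on assumed later uptake and timing. Over equal later uptake of 3% to 20%, the share of control patients with no value falls from 93% to 76%, and power for capped time falls from 70% to 47%. That the subset is selected after randomisation does not depend on these assumptions; the direction and size of any distortion do.

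**What to change.** Add to the Analysis Notes, before the 14-month data are examined:

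- **Outcome 4.** All analysed randomised patients (one per phone number) enter. Time from enrollment to first dose is capped or censored at 14 months. Compare arms by restricted mean time (with complete follow-up, OLS on capped days with robust standard errors, in line with the SAP's other models) or by cumulative incidence by arm. Report days among vaccinated patients as descriptive only.
- **Outcome 6.** Keep the between-dose interval as defined, label it descriptive among two-dose patients, and let outcome 5 carry the randomised comparison.

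The cost is a few sentences and a standard procedure on data already planned. The loss is power if messages only bring forward doses that would have been given anyway, as in case (c); the descriptive report of days among vaccinated patients would still show that pattern.

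There is time. At the SAP date, "We have not yet extracted outcome data as of this writing". The SAP also states: "Our last day of enrolling new patients was 6/27/2025 for appointments on 6/30/2025". Fourteen months from 27 June 2025 is 27 August 2026. For claims, "We will use a 91-day lag to allow sufficient time for claims to be processed", which takes complete timing data to about 26 November 2026. Earlier enrollees reach 14 months sooner, so the rule should be written before any of these data are looked at.
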